11.3.1 Grading of Adverse Event Severity

AEs will be reviewed using the NCI-CTCAE version 5.0 (see [Appendix 5 - Common Toxicity Criteria Gradings](#)). **For AEs not specifically graded by the NCI-CTCAE criteria, the criteria in Table 5 will apply.** For each episode, the highest severity grade attained should be reported.

Table 5: Grading of Adverse Event Severity

Grade 1	Mild; asymptomatic or mild symptoms; clinical or diagnostic observations only; intervention not indicated
Grade 2	Moderate; minimal, local or non-invasive intervention indicated; limiting age-appropriate instrumental activities of daily living*
Grade 3	Severe or medically significant but not immediately life-threatening; hospitalization or prolongation of hospitalization indicated; disabling; limiting self-care activities of daily living**
Grade 4	Life-threatening consequences; urgent intervention indicated
Grade 5	Death related to AE

***Instrumental activities of daily living** refer to: preparing meals, shopping for groceries or clothes, using the telephone, managing money, etc.

****Self-care activities of daily living** refer to: bathing, dressing and undressing, feeding self, using the toilet, taking medications, and not bedridden.

Note: A **severe** AE is not necessarily a **serious** AE. For example, a headache may be severe in intensity, but would not be classified as serious unless it met one of the SAE criteria (see list in [Appendix 4 - Definition of Adverse Events](#))

11.3.2 Relationship of Adverse Event to Study Medication

The Investigator will assess the causality/relationship between FP-1305 and the AE and record that assessment in the source data. Causality will be assessed as:

- **Not related:** AE is obviously explained by another cause; OR the time of occurrence of AE is not reasonably related to administration of the IMP
- **Possibly related:** Study drug administration and AE occurrence are reasonably related in time; AND AE is explained equally well by causes other than the IMP
- **Probably related:** Study drug administration and the occurrence of the AE are reasonably related in time; AND the AE is more likely explained by exposure to the IMP than by other mechanisms

11.4 Serious Adverse Events

The Investigator must report AEs that meet the definition of an SAE (see [Appendix 4 - Definition of Adverse Events](#) for definition) immediately, or **within 24 hours of the trial site becoming aware of the SAE.**

The AEs defined as serious and which require reporting as an SAE must be reported using either an electronic SAE Form in the eCRF (primary) or a paper SAE Form (back-up method; contact details in the form and on the second page of this protocol). If the trial site personnel are unable to complete

the electronic SAE form within 24 h after receiving information about the event, the initial reporting must be done on the paper SAE report and emailed or fax to Simbec-Orion Pharmacovigilance (within 24 h of awareness). The trial site should report the event in the electronic SAE form of the eCRF as soon as possible after that.

The Investigator Site Staff Signature and Task Delegation Log at each trial site will clearly show delegation of responsibilities regarding SAE reporting. A medically qualified person at the trial site identified on the delegation log with this responsibility must assess the SAE. The Principal Investigator or delegated sub-investigators are responsible for the SAE reporting procedures at the site during the trial and must always sign-off on each SAE (regardless of whether reported using the electronic or paper form) as soon as possible even if other site staff have reported the event on behalf of the investigators.

For all SAEs where important or relevant information is missing, active follow-up must be undertaken. The follow-up information of the SAEs must be reported following the same procedure as for the initial reporting. The follow-up report should describe if the SAE has resolved or is continuing, how it was treated, and whether the subject continued the IMP or whether the IMP administration was permanently discontinued.

11.4.1 Monitoring Pregnancies for Potential Serious Adverse Events

Any pregnancy that occurs in a female subject or the partner of a male subject during the trial, must be reported on the Pregnancy Notification Report form in the eCRF (preferred way) or a paper-based form (back-up; contact details on the form and on the second page of this protocol) and must be immediately sent to Simbec-Orion Pharmacovigilance or within 24 hours of the time the information is known.

Pregnancies must be immediately reported and should be followed up to determine outcome, including spontaneous or voluntary termination, details of the birth, and the presence or absence of any birth defects, congenital abnormalities, or maternal and/or new-born complications for up to three months after the birth/termination or if needed, within 1 year after birth where possible and appropriate. Pregnancy in itself is not regarded as an AE.

Consent to report information regarding these pregnancy outcomes should be obtained from the mother. Once consent has been obtained, pregnancy outcomes must be collected for females who took the IMP and the female partners of any males who took the IMP on the Pregnancy Outcome form in the eCRF (preferred way) or a paper-based form (back-up; contact details on the form and on the second page of this protocol) and should be sent to Simbec-Orion Pharmacovigilance immediately or within 24 hours of the time the information is known.

If the pregnancy outcome meets the SAE definition also complete an SAE Form as detailed in [Section 11.4](#). It is important to monitor the outcome of any pregnancies of subjects in order to provide SAE data on congenital anomalies, birth defects or spontaneous abortion.

11.5 Adverse Events of Special Interest

Potential autoimmunity has been reported in study subjects after receiving FP-1305. Four study subjects have had hepatic involvement, with a different clinical presentation and associated AE reporting terminology. Some of these events have been graded life-threatening (more details provided in the IB).

An Adverse Event of Special Interest (AESI) is an AE that requires reporting on an expedited basis (The Investigator must report AEs that meet the definition of an AESI immediately, or within 24 hours of the trial site becoming aware of the AESI to Simbec-Orion Pharmacovigilance and on the eCRF), regardless of the seriousness, expectedness, or relatedness of the AE to the administration of the IMP.

In this protocol, the below listed are considered AESIs for FP-1305:

1. Drug induced liver injury defined by Hy's law as:
 - Grade ≥ 2 alanine aminotransferase (ALT) or aspartate transaminase (AST) increase accompanied with
 - Bilirubin elevation $> 2 \times$ upper limit of normal (ULN) if baseline value was normal; $> 2 \times$ baseline if baseline value was abnormal, without findings of cholestasis or any other reason explaining the combination of increased aminotransferase and serum total bilirubin
2. Any new or worsening of existing autoimmunity after the administration of FP-1305

All AESIs will be followed until recovery or resolution or until the investigator assesses the event to be stable. AESIs will follow the same reporting timeline as that of SAE to pharmacovigilance team.

11.6 AE/SAE Recording and Reporting Period

Details of all AEs will be recorded from the date of consent until the AEs have resolved or no change in the AE status is observed during the post-treatment follow-up period (until Follow-up Visit has been conducted). In circumstances where follow-up visit will not be performed, the follow-up period for AE reporting is 4 weeks from last dose of IMP. If the subject is discontinued from the treatment, the subject must be followed up for open AEs until the AE has resolved, or no change in subject status is observed over the follow-up period. However, all IMP related Grade 3 or 4 AEs must be followed until resolution to Grade 2 or better (for grading see [Section 11.3.1](#)).

The investigator is not required to actively monitor subjects for adverse events occurring after the Follow-up Visit has been conducted; however, serious adverse drug reactions occurring after the follow-up period to a subject that has received one or more doses of the IMP should be reported to the Sponsor per the standard SAE reporting process (see [Section 11.4](#)) within 24 hours of the investigator or site team member becoming aware of them.

Concomitant medications and procedures associated with Serious Adverse Drug Reactions that occur after subject has withdrawn/discontinued (i.e. after Follow-up Visit) will only be recorded in SAE narrative, and not in the other eCRF pages.

11.7 Reporting to Competent Authorities and Independent Ethics Committees

According to the applicable requirements and Safety Management Plan, any AE that meets the criteria of a Suspected Unexpected Serious Adverse Reaction (SUSAR) is subject to expedited reporting to the Competent Authorities and IEC(s)/ IRB(s). The reference safety information (RSI) section in the Investigator's Brochure will be used to assess the expectedness of an SAE.

The Development Safety Update Reports (DSUR) will be provided to the Competent Authorities and IEC(s) /IRB(s) responsible for the trial annually. The DSUR will include information on SUSARs, SARs (serious adverse reactions) and other relevant safety findings.

The relevant Competent Authorities and IEC(s)/IRB(s) will be immediately notified if a significant safety issue is identified during the course of the trial.

11.8 Safety Reporting to Investigators

Details of all SUSARs and any other significant safety issues which arise during the course of the trial and any consequences they may have on the trial will be reported to Principal Investigators. If applicable the Investigator will report the SUSAR or significant safety issue to their IEC/IRB. A copy of any such correspondence should be filed in the ISF.

12 DATA HANDLING AND RECORD KEEPING

12.1 Data Collection

All relevant data related to safety and efficacy including laboratory values and clinical parameters should be recorded in the medical records and be captured in the eCRF system. The site is responsible for completing the eCRF forms in a timely manner. All data on the eCRFs must be verifiable in the source data/hospital or patient records, unless eCRF data are declared as source data.

12.2 Archiving

It is the responsibility of the Principal Investigator to ensure all essential trial documentation and source records (e.g. signed Patient Information and Consent Documents, Investigator Site Files, Pharmacy Files, patients' hospital notes, copies of eCRFs etc.) are stored in secure archives for 25 years after the end of the trial. However, these documents should be retained for a longer period if required by applicable legal requirements. The Sponsor's approval is required prior to transfer or destruction of the documents.

13 QUALITY MANAGEMENT

This trial is to be conducted according to the ICH harmonised tripartite guideline for good clinical practice E6(R2) and the European Union directive 2001/20/EC to ensure that the rights, safety and well-being of trial subjects are protected, consistent with the principles that have their origin in the Declaration of Helsinki (Appendix 3 - WMA Declaration of Helsinki), and that the clinical trial data are credible.

For the trial to start, all required documentation must be approved by the relevant ethical committees and Competent Authorities, in accordance with local legal requirements. The Sponsor must ensure that all ethical and legal requirements have been met before the first subject is enrolled in the trial.

This protocol is to be followed exactly. To alter the protocol, amendments must be written, receive approval from the appropriate personnel, and receive ethical committee/competent authority approval prior to implementation (if appropriate).

Administrative changes (not affecting the subject benefit/risk ratio) may be made without the need for a formal amendment. All amendments will be distributed to all protocol recipients, with appropriate instructions.

13.1 Site Set-up and Initiation

All sites will be required to sign a contractual agreement with the Sponsor prior to participation. In addition, all participating Investigators will be asked to sign the necessary agreements and supply a

current curriculum vitae to the Sponsor or representative of the Sponsor. All members of the site research team that will perform study specific activities will also be required to sign the “Site Staff Signature and Task Delegation Log”. Prior to commencing recruitment, all sites will undergo a process of initiation. Key members of the site research team will be required to be trained by the Sponsor, or a representative of the Sponsor, covering aspects of the trial design, protocol procedures, AE reporting, collection and reporting of data and record keeping. The investigators are responsible for ensuring that appropriate training relevant to the study is given to the medical, nursing and other personnel involved in the study. The investigators will also ensure that any information relevant to the conduct of the study is forwarded to the sub-investigators and other relevant study centre personnel. Sites will be provided with an Investigator Site File and a Pharmacy File containing essential documentation, instructions, and other documentation required for the conduct of the trial. The Sponsor or representative of the Sponsor must be informed immediately of any change in the site research team.

13.2 On-Site Monitoring

A separate Site Monitoring and Management Plan is available where full details of the monitoring activities are described. The trial is conducted according to the GCP and quality standards. Monitors must ensure that the required documentation and trial site training has been done before the site can start enrolling subjects. During the treatment phase, the site(s) will be monitored to ensure protocol adherence and to verify the source data. Any issues in compliance will be reported to the Sponsor.

By participating into this trial, the Investigator(s) and the site(s) conducting this trial will permit trial-related monitoring, audits, Institutional Review Board or equivalent review, and regulatory inspection(s) and provide direct access to source data/documents. A reasonable time must be given for the site(s) to prepare for such activities.

13.3 Audit and Inspection

The Investigator will permit trial-related monitoring, audits, ethical review, and regulatory inspection(s) at their site, providing direct access to source data/documents.

Sites are also requested to notify the Sponsor of any relevant regulatory authority inspections.

13.4 Notification of Serious Breaches

The sites and the Sponsor of the trial will report any serious breaches or protocol/ICH-GCP deviations in accordance with the local laws and current regulations. A “serious breach” is a breach which is likely to effect to a significant degree:

- 1) The safety and rights of a subject.
- 2) The reliability and robustness of the data generated in the clinical trial.

Where the Sponsor is investigating whether or not a serious breach has occurred, sites are also requested to cooperate with the Sponsor in providing sufficient information to report the breach to the relevant Competent Authorities and IEC(s)/IRB(s) where required and in undertaking any corrective and/or preventive action.

14 END OF TRIAL DEFINITION

The end of trial will be the date the overall survival data of the last subject has been collected.

The Sponsor will notify relevant Competent Authorities and IEC(s)/IRB(s) that the trial has ended at the appropriate time and will provide them with a summary of the clinical trial report within 12 months of the end of trial.

The Sponsor reserves the right to stop the trial at any time on the basis of new information regarding safety or efficacy (e.g., discovery of an unexpected, significant or unacceptable risk to the subjects enrolled in the trial), or if trial progress is unsatisfactory (e.g., failure to enrol subjects at an acceptable rate), or for other valid reasons (e.g., Sponsor decides to suspend or discontinue development of the drug). After such a decision is made, the Investigator must inform all on-trial subjects within 1 week. All delivered trial materials must be collected and all eCRF pages completed to the extent possible.

15 STATISTICAL CONSIDERATIONS

This is an adaptive study conducted in 3 parts with separate objectives. For each part there will be a separate statistical analysis plan (SAP) which includes the full details of the analyses of the endpoints of that part. The SAPs can also have sequel documented subversions in case there are analyses conducted intermittently during some part.

15.1 Trial Population

The trial subject population includes subjects who have advanced (inoperable or metastatic) cutaneous melanoma, pancreatic ductal adenocarcinoma, ovarian cancer, colorectal adenocarcinoma, hepatocellular carcinoma, gallbladder cancer, cholangio-carcinoma, uveal melanoma, gastric (including GE junction) adenocarcinoma, ER+ breast cancer and anaplastic thyroid cancer without standard treatment options available and who adhere to the trial inclusion and exclusion criteria.

For the purpose of analyses the following populations are defined:

Safety population: Includes all subjects who have received any amount of FP-1305

DLT evaluable population: Includes all subjects in Part I who have received at least one dose of FP-1305 and followed up for at least three weeks. Any subject that withdraws, discontinues from the trial or dies not related to treatment prior to the end of the 9-week DLT assessment period will be replaced.

Efficacy evaluable population: Includes all subjects who have received at least one dose of FP-1305 for the first time and has tumour imaging conducted at the baseline, and at least once during the treatment or progress or die due to their disease before the first tumour imaging post FP-1305 administration.

Subjects that re-initiate the treatment: Includes all subjects that have received at least one dose of FP-1305 after re-initiation of the therapy and has tumour imaging conducted at the baseline, and at least once during the treatment or progress or die due to their disease before the first tumour imaging post FP-1305 administration will be analysed for efficacy after the re-initiation in a separate cohort.

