15.3.2 Primary Outcome (Part II)

ORR, CBR and irORR will be reported as the proportion of subjects of all evaluable subjects within each tumour type cohort and dose. The 90% confidence intervals for ORR, CBR and irORR will be calculated. Simon's Two-Stage design will be used to evaluate efficacy and decide whether the cohort can be further expanded or not for Part III.

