15.6 Planned Main Analyses

Part I

The main analysis for determining the recommended dose to be expanded upon will take place once all subjects in part I have been recruited to trial and have been followed-up for the 9-week DLT assessment period.

Part II

Each cohort will be analysed when ten evaluable subjects have been accrued and treated with the selected dose. Subjects from Part I can be included into the cohort of ten subjects if they have been treated with the selected dose.

Part III

Each cohort that is continued after the analysis of Part II will be analysed when 29 evaluable subjects have been accrued and treated with optimal dose or until the required 4 responders are reached. The cohort can continue accruing subjects if the stopping rule is not met. The final analysis of each cohort is when the particular cohort has been considered complete.

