15.7 Power Calculations

The operating characteristics of the TITE-CRM will be assessed to assure the design is well calibrated for determining the MTD. Fine-tuning of the model to tailor to the trial's requirements will be aided with the use of the Dose-Transition Pathways, which maps out in advance how the model will recommend doses for all permutations of DLT outcomes for the initial subjects (Yap et al, 2017). Details of the TITE-CRM is presented in the corresponding statistical analysis plan. Part II and Part III are based on adaptive Simon's Two-Stage design, with the following assumptions Type I error rate (α ; one-sided) 0.05, power 0.80, response probability in the palliative treatment 5% (alternative option for these subjects) and response in the trial treatment 20%, 10 subjects in each cohort with at least one subject that demonstrates clinical benefit (CBR by RECIST 1.1 criteria) in the Part II is needed to conclude that the cohort may be expanded. Additionally, data from Part II will be used to determine CLEVER-1 positivity in each of the cohorts. If it is possible that cohorts can be divided in

the CLEVER-1 positive and CLEVER-1 negative groups, both subgroups will be expanded in Part III so that 10 subjects in each group are recruited. In case there are 10/10 non-responders in either of the subgroups, then the recruitment will continue only in the other subgroup with responders. The recruitment can continue within that subgroup until the planned maximum of 29 subjects (or until the required 4 subjects that demonstrate clinical benefit are reached). If the subgroups cannot be defined, the Part III continues with the original cohorts having 1 responder in the cohort. In case there are clearly more negative than positive subjects in some cohort, and also clear difference in the response, the DMC will evaluate the data and decide further cohort expansions.

If the desirable response is obtained in Part III of the trial the cohort(s) may be further expanded.

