12.1 Primary outcome variables

ORR (CR or PR), CBR (CR, PR or SD) and irORR (irCR or irPR) will be reported as the proportion of subjects of all efficacy evaluable subjects within each tumour type cohort and dosing regimen, both at cycle 4 and at cycle 7. The 90% confidence intervals for ORR, CBR and irORR will be calculated. Results from each tumour type (disease group) will be reported separately. There has been

recent debate about the definition of CBR and DCR. Recent article (“Clinical endpoints in oncology - a primer” by Delgado and Guddati) described that for CBR the SD should last at least 6 months. For clarity, and in order to comply with study protocol the tumour imaging results according the RECIST 1.1 will be presented by cycles (doing so there is no difference in the definition of DCR and CBR). Additionally, we are reporting the duration of SD to capture also that utility.

It should be noted that although the protocol states that irORR should be evaluated, it requires confirmation of irCR or irPR from an additional tumour evaluation carried out at least 4 weeks after irCR or irPR was established. However, due practical limitations in the population of subjects recruited for this study, the additional tumour evaluation could not be carried out on several occasions (only single PR result so far) and for this reason, ancillary information (e.g., no signs of clinical progression) will be reported for patients who continue treatment beyond PD.

When progression occurs, patients can continue treatment if IMP still is judged beneficial for the patient, i.e., clinical status does not indicate progression. This will be summarized using the following categories:

- No evidence of progression
- Evidence of progression, IMP still beneficial
- Evidence of progression, patient withdrawn

This presentation will be done for the first tumor imaging and first time of progression for the DCR subjects. Also, the confirmation image result will be reported for patients continuing IMP beyond progression.

Simon’s Two-Stage design will be used to evaluate efficacy and decide whether the cohort can be further expanded or not for Part III. The expansion of each disease group cohort is based on CBR (at cycle 4 or at cycle 7 for the Q3W dosing regimen) and the required proportion to proceed to Part III is 1/10. The same definition, CBR at cycle 4 or at cycle 7, will be used for the classification of subjects (DCR vs non-DCR) in the analyses.

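### Response rates use an evaluable-only denominator that omits some dosed subjects who cannot count as responders, and the documents disagree on whether the Simon rule counts treated or evaluable subjects

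*Protocol*

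**What the plan says.** **Population.** Protocol 15.1, repeated in Part II SAP section 8, defines the efficacy evaluable set as subjects with at least one dose, a baseline scan, and imaging "at least once during the treatment or progress or die due to their disease before the first tumour imaging post FP-1305 administration". Early progressors and disease deaths therefore stay in as failures. A dosed subject with no on-treatment scan and neither of those events falls out.

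**Denominator.** Protocol 15.3.2 has ORR, CBR and irORR "reported as the proportion of subjects of all evaluable subjects within each tumour type cohort and dose". Protocol 15.3.3 does the same for Part III. Part II SAP 12.1 has them "reported as the proportion of subjects of all efficacy evaluable subjects within each tumour type cohort and dosing regimen". SAP 9.1 rules out imputation. No rule counts unscanned subjects as non-responders. SAP section 20 plans a listing of subjects excluded from efficacy but names no all-treated response table.

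**Simon rule.** Protocol 15.7 sets one-sided alpha 0.05, power 0.80, a 5% null and a 20% alternative. Stage 1 needs "10 subjects in each cohort with at least one subject that demonstrates clinical benefit", and the final rule needs 4 among 29.

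**Who is counted.** The text points two ways:
- *Evaluable.* Protocol 15.6: "Each cohort will be analysed when ten evaluable subjects have been accrued", and Part III cohorts are analysed at 29 evaluable. Part II SAP section 4 also expands cohorts to 29 evaluable.
- *Treated or enrolled.* Protocol 1.2 and Part II SAP section 6 cap Part II cohorts at 10 enrolled. Protocol section 4 analyses each cohort once 10 have been treated. Part II SAP section 2 reports 12 cohorts of ten, n=120, and its section 9 calls these subjects enrolled.

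Protocol 15.7 and SAP section 7 give 29 subjects without saying which kind.

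**The concern.** Leaving the efficacy set depends on outcome. A subject without a post-baseline scan cannot contribute a response or stable disease, so each exclusion shrinks the denominator and never the numerator. These are primary efficacy outcomes, and CBR decides which cohorts expand. Safety is summarised on all dosed subjects, so benefit and harm would be reported on different denominators.

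The first scheduled post-baseline scan is at Cycle 4. Three 21-day cycles place it at about day 64, with a window of 10 days either side. That leaves time for withdrawals, toxicity and deaths from other causes.

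The second problem is that the Simon error rates depend on which subjects are counted, and the documents do not settle this.

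**Working it through.** **Inputs.** From Protocol 15.7: p0 = 0.05, p1 = 0.20; continue if at least 1 of 10; succeed if at least 4 of 29. The share of dosed subjects who are not evaluable, d, is not given anywhere, so 5% to 30% is assumed.

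**Step 1: reproduce the stated design.** The probability of success is the sum over x = 1 to 10 of P(X1 = x) × P(X2 ≥ max(0, 4 − x)), where X1 is binomial (10, p) and X2 is binomial (19, p).
- At p = 0.05: x = 1 gives 0.3151 × 0.0665 = 0.0210; x = 2 gives 0.0746 × 0.2453 = 0.0183; x = 3 gives 0.0105 × 0.6226 = 0.0065; x ≥ 4 gives 0.0010. The total is **0.047**.
- At p = 0.20 the same sum is **0.801**.
- Gate alone at 5%: 1 − 0.95^10 = **0.401**.

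A search over two-stage designs meeting these error limits returns this one as the Simon optimal design. The sample size is correct.

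**Step 2: reported rate.** Take 10 treated subjects with one responder. If one unscanned subject is omitted, 1/10 = 10.0% becomes 1/9 = 11.1%. If two are omitted, it becomes 1/8 = 12.5%. With no responders the rate stays at zero.

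**Step 3: rule applied to treated subjects.** If each treated subject has a 5% chance of being a responder, the chance of at least one among 10 treated is still 1 − 0.95^10 = 0.401. Omitting non-responders from the denominator does not change the count that the gate uses.

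**Step 4: rule applied to evaluable subjects.** Accrual continues until 10, then 29, are evaluable, so those lost are in effect replaced. If 5% is the all-treated rate, the rate among those counted is 0.05/(1 − d). Gate passage is 1 − (1 − 0.05/(1 − d))^10, and type I error is the Step 1 sum at that rate.

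| Assumed d | Rate among evaluable | Gate passage | Type I error |
|---|---|---|---|
| 0 | 5.00% | 0.401 | 0.047 |
| 5% | 5.26% | 0.418 | 0.055 |
| 10% | 5.56% | 0.435 | 0.064 |
| 20% | 6.25% | 0.476 | 0.090 |
| 30% | 7.14% | 0.523 | 0.129 |

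**Step 5: cost of counting all treated.** On the first 10 and 29 treated subjects, with unscanned subjects as non-responders, type I error is 0.047 for a 5% all-treated rate, and power is 0.801 if 20% is the all-treated rate. If 20% is instead the rate among evaluable subjects, the all-treated rate is 0.20 × (1 − d):
- d = 5%: rate 19%, power 0.768
- d = 10%: rate 18%, power 0.730
- d = 20%: rate 16%, power 0.640

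**The case against.** **Replacement is not a stated efficacy rule.** A reader might infer that non-evaluable subjects are replaced and that the Simon gate is therefore biased upward. The documents do not support this as a flat statement. The explicit replacement wording in Protocol 15.1 belongs to the DLT population. Replacement in Protocol 4.3.2 also serves DLT assessment, and the replaced subject still counts towards the ten. Replacement for efficacy follows only from the evaluable counts in Protocol 15.6 and SAP section 4. This objection stands, so the gate and type I figures are conditional on that reading.

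**The loss may be small.** Early progressors, disease deaths and anyone with one on-treatment scan are retained. Protocol Table 2 also collects other imaging done by the site. Part I SAP section 12 reports no DLTs in 30 subjects. This stands as a limit on size: nothing supports 30% in particular. It does not show the loss to be zero, since withdrawals and non-disease deaths count too. Protocol 11.5 also reports four subjects with hepatic involvement and some life-threatening events, without giving their timing.

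**The null may refer to evaluable subjects.** Protocol 15.7 does not say. If it does, type I error remains 0.047. This stands, and it is one more thing to state.

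**The consequence is limited.** Expansion is permissive, the SAP calls its analyses exploratory, and the listings of exclusions and of response by cycle would let a reader rebuild an all-treated rate. That lowers the stakes but does not replace a planned analysis. Part III has its own SAP, which was not available, so the 29-subject figures rest on the protocol alone.

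**Conclusion.** The denominator point holds under every reading: reported ORR, CBR and irORR can only equal or exceed the all-treated rates. In a cohort of ten with one responder, each early loss adds about 1 percentage point.

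The effect on the Simon rule is conditional on three things: the evaluable count in Protocol 15.6 governs, the 5% null refers to all treated subjects, and some dosed subjects are lost. Under those conditions gate passage at 5% moves modestly, from 0.401 to 0.435 at 10% loss. Type I error exceeds the stated 0.05 even at 5% loss (0.055) and reaches 0.129 at 30%. Under the treated reading the gate is unchanged.

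The correction is worth making, although its size in this trial is unknown.

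**What to change.** 1. Reconcile Protocol 1.2, section 4, 15.6 and 15.7 with Part II SAP sections 4, 6 and 7, so that one count, treated or evaluable, drives the 10- and 29-subject analyses. State which population the 5% and 20% refer to.
2. Amend Protocol 15.1, 15.3 and 15.6 and Part II SAP sections 8 and 12.1 so that the primary denominator for response rates and Simon decisions is all dosed cohort subjects. Subjects without a post-baseline assessment count as non-responders.
3. Keep the efficacy evaluable set as a sensitivity analysis, with the number excluded and the reasons tabulated by cohort.

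**Cost.** No new data are needed, but protocol text changes as well as the SAP, and one response table is added. Reported rates will be equal or slightly lower. If 20% was meant as a rate among evaluable subjects, power falls from 0.801 to 0.768, 0.730 or 0.640 at 5%, 10% or 20% loss, and the amended text should say so.
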